The Russian multicenter observational study of ACS patients with at least one-year follow-up -the ORACLE (ObserveRvation after Acute Coronary syndrome for deveLopment of trEatment options) study

Protocol

Version 1 oct 2016

TABLE OF CONTENT

1. Introduction
2. The aim of the study
3. Study design and patient selection
4. Carried out during the study treatment
5. Study procedures
6. End-points
7. Collection and analysis of statistical data.
8. Ethical and legal aspects.
9. Data ownership and use of research results.

SUPPLEMENT

1. Informed consent to participate in Clinical Research Participation
2. Terms of patients numbering and labeling of genetically tubes
3. Right to seize, storage and transportation of blood

ABBREVIATIONS

ACS Acute Coronary Syndrome

AS acute stroke

CABG Coronary artery bypass grafting

CRF Case report form

CAG coronary angiography

CHD – coronary heart disease

CPK Creatine phosphokinase

CPK-MB Creatine phosphokinase-MB

ECG electrocardiogram

MI Myocardial Infarction

PCI Percutaneous Coronary Intervention

TIA transitory ischemic attack

Tn troponin

UA unstable angina

Introduction

The role of genetic factors in the development of CHD exacerbations studied not enough. Most research in this area planned and carried out on a "case-control". Using a similar protocol entails significant errors are associated with a high incidence of subclinical atherosclerotic vascular lesions. Moreover, much of atheroma is extravasal, making it impossible to identify them by angiography. Therefore, necessary to conduct prospective studies to estimate the frequency of so-called hard endpoints. Previously, similar trials were conducted, mainly in connect with drug approving procedures. The spread data from them to other patients directly is not entirely justified. At the same time, the influence of genetic factors in this group of patients can be substantial.

In the previous part of the study, the sample of patients of Moscow, St. Petersburg, Kazan, Chelyabinsk, Stavropol, Perm, and Rostov-on-the-Don was formed, of 1,200 people admitted due to acute coronary syndrome (ACS) including unstable angina and acute myocardial infarction, at coronary care units with follow-up for three years. We found several factors, including genetic, that significantly affect the outcomes of the disease. Coronary atherosclerosis and its complications now considered as a multifactorial disease associated with inherent factors. Therefore, the project provides, besides accounting a significant amount of clinical and instrumental data, the determination of a wide range of genotypes and alleles of polymorphic markers candidate genes encoding the protein factors of the hemostatic system, enzymes of lipid metabolism system, and anti-inflammatory cytokines. It is assumed that the prediction outcomes of coronary heart disease should be carried out taking into account the fact that several factors (gender, diabetes, age, aortic stenosis, atrial fibrillation, etc.) can not only significantly change the forecast itself but also affecting the significance of other risk factors. Since the last study, the standards significantly of ACS management changed. Invasive treatment not only creates opportunities to reduce coronary mortality but also increased demands on the patient's adherence to the assigned medication and creates additional risks associated with its activity (especially with an antithrombotic treatment activity). In these circumstances, the development of personalized approaches to prescribing drugs is particularly important. Thus, the prediction of coronary heart disease outcomes after an ACS on a set of clinical, instrumental, biochemical and genetic indicators is of great importance, as it allows to plan the most optimal treatment for the individual patient.

1. THE AIM OF THE STUDY

To develop a model of individualized risk of coronary heart disease outcomes and side effects of therapy based on clinical and instrumental, biochemical, and genetic parameters in patients with ACS.

2. STUDY DESIGN AND PATIENT'S SELECTION

2.1. STUDY DESIGN

This is the Russian multicenter observational study of ACS patients with at least one-year follow-up. We planned to include 1700 ACS patients admitted to invasive hospitals. The follow-up will continue until at least 200 deaths for any reason.

2.2. INCLUSION CRITERIA

- ACS patients with indications for PCI hospitalization, regardless of whether or not carried out PCI.
- Signed informed consent to participate in the study.

2.2.1. INCLUSION CRITERIA FOR ACS PATIENTS WITHOUT SEGMENT ST ELEVATION

- All patients meet the criteria of very high, high, or intermediate risk and selected low-risk patients according to current guidelines.

1.1.1. THE INCLUSION CRITERIA FOR PATIENTS WITH ACUTE CORONARY SYNDROME WITH ST ELEVATION OR ALREADY FORMED LARGE MYOCARDIAL INFARCTION

Patients who have been hospitalized with symptoms caused by acute myocardial (heart attack prescription no more than 10 days, hospitalization time) and at least one of the following additional criteria identified at admission:

- elevation ST: ST persistent increase 1 mm in two contiguous leads limb or ST rise to 2 mm in two adjacent precordial leads
- the emergence of a new blockade of left bunch branch block
- dynamics of acute myocardial infarction (appearance of pathological Q, reduction of R, change the final portion of the ventricular complex)

1.2. EXCLUSIONARY CRITERIA

- The lack of patient consent for participation in the study
- Inability to contact with the patient after discharge

2. TREATMENT

All patients should receive the standard treatment for acute coronary syndrome and related diseases according to the current guidelines.

3. STUDY PROCEDURES

3.1. THE SEQUENCE OF STUDY

Stationary Phase

1st day:

Symptoms of acute coronary syndrome, leading the patient to the hospital
Conformity assessment criteria for inclusion in the study

Written informed consent

blood samples for genetic analysis

Filling Case Report Form (CRF)

2nd - 5th day

Filling in the missing information in the CRF

During the CAG or PCI is an extensive video research and filled with a separate PCI card

Upon cancellation of the CAG and PCI card is filled with the count of "rejection reason "

Register endpoint - filling in the relevant sections of the CRF
discharge planning

6th day - discharge from the hospital

Echocardiography - attached full movie, and is filled with a special card echocardiogram

Final inspection and afterfilling CRF

Talk with the patient follow-up plan

The introduction of information into an electronic database

Sending information to the Coordination Center for Research

Outpatient treatment stage

25 ± 5 days from the date of inclusion (but no earlier than 5 days after discharge)

Telephone contact with the patient or his relatives

Register endpoint and adherence to treatment - filling in the relevant sections of the CRF

90 ± 15 days from the date of inclusion

Telephone contact with the patient or his relatives

Register endpoint and adherence to treatment - filling in the relevant sections of the CRF

180 ± 15 days from the date of inclusion

control monitoring visit

ECG

Register endpoint and adherence to treatment - filling in the relevant sections of the CRF.

365 ± 15 days from the date of inclusion

Telephone contact with the patient or his relatives.

Register endpoint and adherence to treatment - filling in the relevant sections of the CRF

Next phone contacts 1 time in 6 months to achieve thereof, the observation of the last patient included in the study (or up to 200 deaths, if for the planned observation period their number was less).

The final filling of card and electronic form, sending the information to the coordination center.

Appropriate CRFs and forms for the events should be completed in accordance with the instructions in the manual of the researcher.

In the case report of the patient information is recorded on the adverse clinical outcomes that have developed since the last contact with the patient (see. the relevant section of the CRF). Also recorded group of drugs, which the patient took over this time period.

4. ENDPOINTS

4.1. The primary endpoint

- Dearth from any causes

5.2. Secondary end-points

1. cardiovascular (atherothrombotic) events (cardiovascular death, non-fatal myocardial infarction, non-fatal stroke)
2. non-fatal myocardial infarction
3. recurrent acute coronary syndrome (all cases of recurrent myocardial infarction or unstable angina after the index events)
4. recurrent PCI (all cases of recurrent PCI after the index hospitalization)
5. complicated atherosclerosis
6. non-fatal stroke

5.3 Other Pre-specified Outcome Measures:

1. Bleeding

all cases of bleeding during and after the index hospitalization

6.3. Defining endpoints

6.3.1. Acute myocardial infarction

any two of the following criteria meets the diagnosis of acute, evolving or recent myocardial infarction:

typical dynamics of biochemical markers of myocardial necrosis to a value above the upper limit of normal two (or if the markers have increased by more than 50% of the minimum level of detection of the enzyme) and at least one of the following:

- a) symptoms of ischemia
- b) The appearance of pathological Q wave on ECG
- c) ECG changes indicating ischemia (increase or decrease of ST segment)
- d) Coronary intervention or pathological evidence for acute myocardial infarction

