4.1.1. Previous myocardial infarction

The emergence of new wave Q on an electrocardiogram (ECG compared to the previous visit), the appearance of new zones in the a- or dyskinesia echocardiogram.

Documented in another hospital myocardial infarction.

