4.1.2. Unstable angina

It is defined as a recurrent chest pain / symptoms of ischemia, continuing for more than 5 minutes, with documented typical ECG changes indicative

of ischemia and / or improving cardiac enzymes and markers of myocardial damage and require hospitalization.

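### The acute MI definition opens with an any-two rule but then requires a marker rise, so symptoms with ST change and no marker rise may or may not count as non-fatal MI

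*Combined protocol and SAP*

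**What the plan says.** Section 6.3.1 (Acute myocardial infarction) begins: "any two of the following criteria meets the diagnosis of acute, evolving or recent myocardial infarction". What follows is a single compound criterion. It describes marker dynamics with thresholds, ends with "minimum level of detection of the enzyme) and at least one of the following", and then lists four items: a) ischaemic symptoms, b) a pathological Q wave, c) "ECG changes indicating ischemia (increase or decrease of ST segment"), and d) coronary intervention or pathological evidence.

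Section 4.1.2 (Unstable angina) describes recurrent chest pain or ischaemic symptoms "continuing for more than 5 minutes, with documented typical ECG changes indicative" of ischaemia and/or marker changes, requiring hospitalization. It does not say that the MI criteria must be unmet.

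Section 4.1.1 (Previous myocardial infarction) also stands among the endpoint definitions. It gives routes with no marker requirement: "The emergence of new wave Q on an electrocardiogram (ECG compared to the previous visit"), new wall-motion abnormality on echocardiography, or "Documented in another hospital myocardial infarction".

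Section 5.2 makes non-fatal MI secondary endpoint 2 and a component of secondary endpoint 1, "cardiovascular (atherothrombotic) events (cardiovascular death, non-fatal myocardial infarction, non-fatal stroke"). Unstable angina enters neither. Both MI and unstable angina enter secondary endpoint 3, "recurrent acute coronary syndrome (all cases of recurrent myocardial infarction or unstable angina after the index events").

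**The concern.** The opening sentence of section 6.3.1 and the list beneath it do not state the same rule. The opening sentence treats the criteria as interchangeable; the list makes the marker rise a condition. A site that follows the opening sentence can record MI for an episode of symptoms with ST change and normal markers. A site that follows the list cannot.

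That episode is also a typical case of unstable angina under section 4.1.2. Recurrent unstable angina is an expected event in a cohort recruited for ACS. The reading adopted therefore decides whether such an event enters secondary endpoints 1 and 2.

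The study is multicentre, its aim is a risk model for coronary outcomes, each research group may publish its own data, and no central adjudication of events is described. If centres read the definition differently, MI will not mean the same thing across the dataset, and any model with MI in its outcome would absorb that difference.

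**Working it through.** The plan gives no figure to reproduce here, so the check is a comparison of the wordings.

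**Step 1: where the two wordings differ.** Let M = 1 if the marker criterion of section 6.3.1 is met and 0 if not, and let n be the number of items a to d that are met.

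- Opening sentence, with the marker and a to d counted individually: MI if M + n ≥ 2.
- List: MI if M = 1 and n ≥ 1.

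If M = 1, the opening sentence needs n ≥ 1, which is the list's rule, so the two agree. If M = 0, the opening sentence needs n ≥ 2, and the list never gives MI. The wordings are therefore nested: every MI under the list is an MI under the opening sentence. They disagree exactly when M = 0 and n ≥ 2.

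**Step 2: the case that matters most.** Take symptoms (a) and ST change (c), no marker rise, and neither b nor d. Then M = 0 and n = 2, so M + n = 2. This is MI under the opening sentence and not MI under the list.

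**Step 3: the same case under section 4.1.2.** If the symptoms exceed 5 minutes and hospitalization is required, the ECG branch alone makes the event unstable angina. The unclear wording of the enzyme branch is not needed.

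**Step 4: the endpoints in section 5.2.** For a surviving patient after the index event:

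| Symptoms + ST change, no marker rise | Reading of 6.3.1 | Class | Endpoint 1 | Endpoint 2 | Endpoint 3 |
|---|---|---|---|---|---|
| Over 5 min and hospitalized | Opening sentence | MI (also meets unstable angina) | yes | yes | yes |
| Over 5 min and hospitalized | List | Unstable angina | no | no | yes |
| Shorter, or not hospitalized | Opening sentence | MI | yes | yes | yes |
| Shorter, or not hospitalized | List | Neither | no | no | no |

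Endpoints 1 and 2 move in both situations. Endpoint 3 stays fixed only when the duration and hospitalization conditions hold.

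**Step 5: other analyses.** Death from any cause uses none of these definitions. The outcome list in the statistical section (Collection and analysis of statistical data) does not name non-fatal MI. It names all cardiovascular events, which would be affected if that means the composite in section 5.2; the document does not say whether it does.

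**Step 6: section 4.1.1.** A new Q wave without a marker rise matches this section whichever reading of 6.3.1 applies. Section 3.1 schedules an ECG at the day-180 visit, so such a finding can arise in follow-up. The document does not say whether it is then an endpoint MI or only a record of a past one.

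**The case against.** The strongest reply is that these are not two competing rules. Section 6.3.1 sets out one compound item with a to d beneath it, and any two can loosely mean the marker plus one of a to d. Counting a and c alone as MI requires ignoring the connector that ties a to d to the marker. Much of this stands: the rules are nested, the marker-required reading is the more natural one, and the lead-in looks like loose or poorly translated wording. But the lead-in is still part of a stated endpoint definition, following it literally gives a different result, and no other section says which wording governs.

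Second, section 3.1 sends event forms to a researcher manual, which may hold the rule. That is possible and cannot be checked here. If so, the rule belongs in the protocol as well.

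Third, the consequence is narrow: the primary endpoint is untouched, and the outcome list in the statistical section does not name non-fatal MI. Both points stand and limit the weight of the concern.

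Fourth, the missing exclusion in section 4.1.2 changes endpoints 1 and 2 by itself only if each event receives a single code, which the document neither requires nor rules out. That is fair; the exclusion supports the main correction and is not a separate fault.

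A reader might also infer that a definable share of MI events is misclassified, by counting combinations of criteria on which the wordings disagree. The document does not support this. Such counts depend on which criteria are held fixed and how many marker levels are allowed, and they say nothing about how often each combination occurs.

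**Conclusion.** The definition in section 6.3.1 is internally inconsistent, and the inconsistency reaches secondary endpoints 1 and 2. It is confined to events without a qualifying marker rise that meet at least two of a to d. The main example is symptoms with ST change, which section 4.1.2 would class as unstable angina if the episode lasts more than 5 minutes and requires hospitalization.

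Two further inferences go too far. One is that recurrent ACS is immune because it pools MI and unstable angina: for ST-change events this holds only under those duration and hospitalization conditions. The other is that the planned analyses are necessarily affected: for the outcomes listed in the statistical section, this depends on all cardiovascular events meaning the section 5.2 composite.

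The number of affected events cannot be derived, since the document gives no rate of MI or unstable angina. The conclusion assumes that the researcher manual does not already settle the rule, and takes a qualifying marker rise to be whatever threshold section 6.3.1 intends. The point should be corrected, but it does not threaten the primary endpoint.

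**What to change.** - **Section 6.3.1:** delete the any-two condition from the opening sentence, so that acute MI means the marker criterion plus at least one of a to d.
- **Section 4.1.2:** add that unstable angina applies only when the MI criteria are not met, so that MI takes precedence.
- **Section 4.1.1, as a secondary clarification:** state whether a new Q wave, new wall-motion abnormality on echocardiography, or an MI documented at another hospital counts as an endpoint MI during follow-up. The exclusion added to 4.1.2 should refer to the same set of MI criteria.

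If the researcher manual already contains these rules, copy them into the protocol; if not, change both documents together.

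The cost is a wording change and some recoding of recorded events where marker and ECG data can be obtained. That will not always be possible: apart from the day-180 visit, scheduled follow-up in section 3.1 is by telephone, and nothing there requires sites to retrieve records from other hospitals. Events without the necessary records should be reported as not classifiable, with their number shown, and not assigned by default to MI or unstable angina.

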4.1.1. Previous myocardial infarction

The emergence of new wave Q on an electrocardiogram (ECG compared to the previous visit), the appearance of new zones in the a- or dyskinesia echocardiogram.

Documented in another hospital myocardial infarction.

4.1.2. Unstable angina

It is defined as a recurrent chest pain / symptoms of ischemia, continuing for more than 5 minutes, with documented typical ECG changes indicative

of ischemia and / or improving cardiac enzymes and markers of myocardial damage and require hospitalization.

4.1.3. Fatal case

All cases of death will be merged the concept of "total mortality" and will be divided according to the genesis of "due to cardiovascular disease" and "not associated with cardiovascular disease," according to information provided to the physician-researcher. Fatal, "due to cardiovascular disease," it will be divided according to the genesis of "cardiovascular mortality" and mortality from "other cardiovascular disease." Death as a result of acute myocardial infarction, CABG, sudden cardiac death will be classified as "cardiovascular mortality." The category of death from other cardiovascular diseases will be charged any additional cases related to the cardiovascular system (ie, death from stroke, major bleeding, pulmonary embolism, as a result of the operation). For the category "non-cardiovascular disease deaths" are referred all cases of clearly non-cardiac origin (eg, death from cancer, injuries, infections, etc.).

4.1.4. Stroke, TIA

is defined as the presence of a new focal neurologic disorder considered vascular in origin, with signs or symptoms continued more than 24 hours. Stroke is classified as ischemic, haemorrhagic or indeterminate type.

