4.1.6. Coronary revascularization

Taking into account all the cases of revascularization procedures

5. COLLECTION AND ANALYSIS OF STATISTICAL DATA.

Statistical analysis was performed using a standard statistical package IBM SPSS Statistics Version 22 for Windows and MedCalc software version 18.3. It involves analysis of clinical predictors

- all cause mortality
- cardiovascular mortality
- all cardiovascular events
- stroke
- any, significant and major hemorrhage

For continuous variables will be analyzed and the distribution criteria for its compliance with the normal using the Kolmogorov-Smirnov test. To describe the features of the normal distribution using the mean with standard deviation

indication ($M \pm SD$). For signs with non-normal distribution when reporting the results indicate the median and interquartile range - the 25th and 75th percentiles ($Me (Q1-Q3)$). Discrete values are calculated as a percentage, the significance of differences were compared by Pearson criterion χ^2 . Comparison of quantitative traits obeying the normal distribution, is carried out using t-criterion Student, unnormal distribution - by using the non-parametric test, the Mann - Whitney and Kruskal - Wallis test for unrelated groups. For quantitative evaluation of the values calculated correlation coefficient is obtained and the accuracy depending on the Pearson's criteria (normal distribution) or Spearman (with a deviation from the normal distribution) for bilateral hypothesis testing criterion. The rating values of the predictor is conducted by plotting ROC curve and calculating the area under the curve (AUC). Treatment Evaluation of Frequency Allocations alleys and genotypes studied these genes will be performed using "Gene Expert" unified program. Genotype frequency distribution was calculated (the Hardy-Weinberg equilibrium test), genetic risk of NO using multiplicative general, dominant and recessive inheritance models. To assess the effect of clinical factors on the independence of the risk of adverse outcomes is performed using the Kaplan-Meier method using the log-rank test (Log Rank) and using Cox regression.

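### The stroke definition has no alternative for death within 24 hours, so the unqualified stroke outcome in section 5 may miss the earliest fatal strokes; its heading also names TIA, which cannot meet it

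*Combined protocol and SAP*

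**What the plan says.** Section 4.1.4 is headed "4.1.4. Stroke, TIA" and gives a single definition: a "new focal neurologic disorder considered vascular in origin, with signs or symptoms continued more than 24 hours". Nothing is added for a patient who dies before 24 hours have passed. The sentence that follows, "Stroke is classified as ischemic, haemorrhagic or indeterminate type", concerns stroke only. TIA gets no criterion of its own. The abbreviation list expands it ("TIA transitory ischemic attack") but gives no duration.

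Four other places bear on the point:

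- **Section 5.2, Secondary end-points.** Stroke appears twice, each time as non-fatal: as a component of the composite in item 1, and alone as "6. non-fatal stroke".
- **Section 4.1.3, Fatal case.** Deaths due to cardiovascular disease are split in two. Myocardial infarction, CABG and sudden cardiac death make up *cardiovascular mortality*. A second category, for other cardiovascular diseases, takes "death from stroke, major bleeding, pulmonary embolism, as a result of the operation". Neither category has a time limit.
- **Section 5, Collection and analysis of statistical data.** The outcome list follows the words "It involves analysis of clinical predictors". It contains all-cause mortality, cardiovascular mortality, all cardiovascular events, stroke, and haemorrhage. Stroke carries no qualifier.
- **TIA** is in neither the endpoint lists nor the section 5 list.

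**The concern.** A definition that rests only on duration excludes a patient who does not live long enough to meet it. Someone who dies 10 hours after onset has had no signs for more than 24 hours. Applied literally, the rule says that this patient had no stroke.

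The error would have a direction, because it removes the most rapidly fatal strokes and puts them with the patients who had no stroke. Section 5 compares patients with favourable and unfavourable outcomes and builds the prognostic function by logistic regression. The study aims to predict side effects of therapy as well as disease outcomes, and the introduction stresses the risks of antithrombotic treatment. Losing the earliest fatal strokes from a stroke model runs against that aim.

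The TIA problem is different. The heading makes TIA a subject of the definition, yet in its usual meaning (resolution within 24 hours) it can never satisfy it. A site guided by the heading may register a TIA in this part of the CRF, while a site guided by the text will not.

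**Working it through.** The plan states no stroke rate, event count or power for stroke, so there is no figure to reproduce. The check is to follow one case, a stroke fatal at 10 hours, through each outcome as written.

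| Outcome | Is the case counted? | Does the missing death clause decide it? |
|---|---|---|
| Primary endpoint, death from any cause | Yes | No |
| Non-fatal stroke, alone (5.2, item 6) | No, because it is fatal | No |
| Non-fatal stroke within the composite (5.2, item 1) | No, because it is fatal | No |
| Death from stroke, under other cardiovascular diseases (4.1.3) | Yes, with no time limit | No |
| *Cardiovascular mortality* (section 5 list, defined in 4.1.3) | No, read literally: stroke is not among its named causes | No |
| Stroke (section 5 list) | No, if 4.1.4 is applied literally | **Yes, if this outcome means all strokes** |

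Only the last row turns on the missing clause. Whether section 5 means all strokes is not stated. The contrast in wording points that way: section 5.2 writes "non-fatal stroke" where it means that, and section 5 does not. On that reading the patient is absent from both the stroke and the cardiovascular mortality outcomes of section 5. Of the outcomes listed there, only all-cause mortality is certain to include the case. A haemorrhagic stroke might also enter the haemorrhage outcome, but the plan does not say so.

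**Possible size.** The one input from the documents is the planned sample of 1700 (section 2.1). The rates are assumptions.

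- Strokes, if 2-4% of patients have one: 1700 × 0.02 = 34; 1700 × 0.04 = 68.
- Deaths within 24 hours, if 5-10% of strokes: 34 × 0.05 = 1.7; 68 × 0.10 = 6.8.
- Result: about 2-7 strokes coded as no stroke, which is the assumed 5-10% of the total.

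**TIA.** Signs must last more than 24 hours, and a TIA in the usual sense resolves before then. The heading and the definition therefore do not match. Because TIA feeds no endpoint and no analysed outcome, the mismatch has no direct numerical consequence when the text is followed.

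**The case against.** The strongest objection is that no declared endpoint loses an event through the missing clause. A reader might infer that the secondary stroke endpoints are depleted of early fatal cases. They are not: items 1 and 6 of section 5.2 exclude every fatal stroke by name, whatever its timing, and a death clause would leave them unchanged. The deaths also remain in the primary endpoint and in the death-from-stroke category. All of this stands, and it confines the point to a single entry in section 5.

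That entry may be shorthand for non-fatal stroke. If so, the loss disappears and what remains is a failure to say which is meant. The documents do not settle this. The difference in wording favours all strokes but does not prove it.

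A reader might also infer that TIAs inflate the non-fatal stroke counts. The documents do not support that. The written criterion already excludes a TIA, so inflation would need sites to depart from the text and then record a TIA as a stroke. Assuming 0.3-0.5 TIAs per stroke and half the sites registering them gives 15-25% of the stroke count (0.3 × 0.5 to 0.5 × 0.5), but this only restates the assumptions. Event forms also follow an investigator manual that is not among the documents, so how sites actually code TIA cannot be judged here.

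Finally, it is tempting to say that factors which make a stroke rapidly fatal would look neutral or protective for stroke. With 90-95% of strokes still counted under the assumptions above, and no calculation behind the statement, that goes too far.

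**Conclusion.** The concern holds in a limited form. Section 4.1.4 states a rule that, read literally, codes a stroke fatal within 24 hours as no stroke. This affects the stroke outcome of section 5 if that outcome means all strokes. It does not affect the primary endpoint, the non-fatal stroke endpoints, or the recording of stroke deaths under section 4.1.3.

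The size cannot be derived from the documents. It is probably a few events: about 2-7, given 1700 patients and the assumed stroke and early-fatality rates.

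The TIA heading is a real mismatch that invites inconsistent coding. That conclusion takes TIA in its usual meaning, since the documents give no duration, and no effect on any endpoint can be shown.

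Section 4.1.3 raises a separate question: it places stroke death at any time outside *cardiovascular mortality*. If cardiovascular death in the section 5.2 composite means that category, fatal strokes drop out of the composite too. Changing the stroke definition would not repair this.

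**What to change.** Make three wording changes:

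1. In section 4.1.4, define stroke as a new focal neurologic disorder of vascular origin with signs or symptoms for more than 24 hours, or ending in death before 24 hours.
2. In section 5, state that the stroke outcome includes fatal and non-fatal stroke. If the sponsor intends only non-fatal stroke, section 5 should say that instead; the first change would then not alter that outcome.
3. Remove TIA from the heading of section 4.1.4, or define it separately as an event that is recorded but not counted as stroke.

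A matching CRF instruction is needed. No procedure is added for patients or sites. The cost is re-checking events already registered under this section, both early deaths attributed to stroke and any TIA entries.
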